10.4 Dose Escalation/Finding Schema

The FDA approved porfimer sodium dose (2 mg/kg) will not change. We will aim to deliver light fluence rate of ≥ 8.6 mW/cm² and fluence of ≥ 45 J/cm² to 100% of the CTV (dose level 1), as much as possible. Dose level -1 will ≥ 5.0 mW/cm² and fluence of ≥ 45 J/cm² to 100% of the CTV.

Table 2. The study plan for finding optimal fluence rate in I-PDT with Photofrin in patients with LAHNC.			
Dose Level Number of patients with DLT at a given dose level		Decision rules	
Dose Level 1 (Starting): The maximum fluence rate, scaled for	0 out of 3	Enter 3 patients at Dose Level 1 : The laser fluence rate and fluence, scaled for human, which induced maximum photoreaction in the animal models	
human, which induced effective	1 out of 3	Enter 3 more patients at this Dose Level .	

photoreaction in the animal models.	≥2	Enter 3 patients at Dose Level -1 : The laser fluence rate and fluence, scaled for human, which induced minimal toxicity in the animal models.
	≤ 1 out of 6	This is generally the recommended Phase II dose rate/dose. At least 6 patients must be entered at the recommended Phase II dose.

In participants where their tumors may require more than one course of I-PDT for complete effective illumination of the CTV, up to three sessions of I-PDT may be performed, at the discretion of the treating physician. The FDA approves to administer up to three courses of PDT with Photofrin® each separated by at least 30 days in the treatment of esophageal and endobronchial cancer (http://www.photofrin.com/wp-content/uploads/2013/02/prescribing-info.pdf.). Therefore, treatment sessions in this study will be conducted at least 30-days apart. The porfimer sodium dose (2 mg/kg) will remain the same.

See Appendix D 1 for the Dose Escalation Schedule of Events. The date of the last I-PDT course will be used to determine the scheduling of the follow up SoC related to this study.

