 - 10. If possible, intraoperative CT (such as O arm) or another radiological imaging (e.g. C-arm) will be used to image the catheters in the tumor.
 - 11. Refer to Section 10.2.1.
 - 12. Medications ongoing within 1 week prior to porfimer sodium injection.
 - 13. AE reporting period will be for 30 days \pm 2 days post first SOC treatment.
 - 14. First SOC treatment day of I-PDT day if no therapeutic SOC treatment is administered.
 - 15. Refer to Section 11.6f patient doesn't come in or quality of life is missed, may be done via telephone.
 - 16. In the event that the tumor size is such that treating the entire tumor could cause a health risk to the patient, the current I-PDT course will be broken up into session/s. We will illuminate one part of the tumor on the day of I-PDT and another part/s of the tumor in additional I-PDT session/s within 14 days after the initial I-PDT session, at the discretion of the treating physician. If

- an I-PDT course is broken up into I-PDT sessions, the I-PDT dosage for each session will remain the same as though sessions were not broken up as dosing is dependent on number of fibers received per session. The patient will not need to receive additional doses of porfimer sodium if having additional I-PDT sessions within 14 days after the previous I-PDT session as porfimer sodium is expected to be in the tumor for at least 30 days.
- 17. Another (one or two, total of three) laser light treatment(s) only (no additional drug) within 2-3 weeks of the initial administration of Photofrin.
- 18. Patient may receive a second complete I-PDT treatment that will include drug and light administration. It will be at the discretion of the treating physician to administer this additional treatment. Another CT (charged to the study if it is not SoC) will be done, and all tests will be conducted before and after additional treatment, according to the same schedule parameters as the initial treatment.

Appendix D 1 Schedule of Procedures and Observations (Only for Dose Escalation later I-PDT Sessions if Deemed Necessary by Physician)**

Evaluation	Repeat of Initial Tests and Procedures ^A	Pre- Operative	Day of Treatment	1-week Post- treatment	Clinic Visit	Post- Treatment	Follow- Up
Physical Exam/ Vital signs ^B & pain assessment using a verbal score 0-10	X			X	X	X	X
Hematology ^C and Chemistry ^D	X			X	X	X	
Research Blood Draws ^E			X	X	X	X	X
Pregnancy Test (Urine)	X						
ECOG Performance Status	X		X	X	X	X	X
UW-QoLQ v. 4 ^p	X			X	X	X	X

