Fresh Tissue Tumor Biopsy ^F	X			X			
Standard Imaging of the head and neck with CT or MRI ^G	XH						XI
Treatment planning	X						
Porfimer Sodium administration and Vital Signs		X^{J}					
Intraoperative Ultrasound ^Q			X				
If possible, intraoperative CT or other clinically approved radiological imaging			X ^K				
Interstitial PDT (I-PDT)			$X^{L, Li}$				
Concomitant Medications	X ^M		X				
Standard of care (SoC) chemotherapy, targeted therapy or potentially immunotherapy as first line palliative care treatment options					X ^N		
Adverse Events ^O	X ^{Oi}		X	X	X	X	

Notes:

^{*} The I-PDT procedure is termed a "course". As per later Section 10.4, study participants may have up to 3 I-PDT courses per physician's discretion, at least 30 days from the previous illumination procedure.

- ** NOTE: 2nd and 3rd I-PDT courses are per the physician's discretion as per Section 10.4, 2nd and 3rd I-PDT courses are not required for all study participants. If it is decided participants should receive all 3 I-PDT courses, items from "Repeat of Initial Tests and Procedures" until the completion of I-week Post treatment" are completed twice before the Clinic Visit and start of Standard of Care chemotherapy.
 - A. Performed within 4 weeks prior to 2nd and 3rd I-PDT courses. Since there may be up to three I-PDT courses, at least 30 days apart (see Section 10.4) per the physician's discretion, the initial procedures, exams, or tests may be completed up to two more times based on the individual participant's study treatment regimen. Research blood draws, standard imaging of head and neck with CT or MRI, and treatment planning for later I-PDT courses are per physician's discretion.
 - B. Temperature, heart rate, respiratory rate, blood pressure, and body weight. Refer to Section 11.2.
 - C. Hematology (i.e., CBC (with auto differential), ANC, and platelets). Refer to Section 11.2.
 - D. Chemistry (i.e., AST, ALT, total bilirubin, alkaline phosphatase, creatinine, potassium, glucose, and calcium). Refer to Section 11.2.
 - E. This is optional. Research blood draws for any 2nd and 3rd I-PDT courses (all timepoints) are per the physician's discretion. Refer to immune markers Section 11.8 (1 green top tube).

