- P. In the event that the tumor size is such that treating the entire tumor could cause a health risk to the patient, the current I-PDT course will be broken up into session/s. We will illuminate one part of the tumor on the day of I-PDT and another part/s of the tumor in additional I-PDT session/s within 14 days after the initial I-PDT session, at the discretion of the treating physician. If an I-PDT course is broken up into I-PDT sessions, the I-PDT dosage for each session will remain the same as though sessions were not broken up as dosing is dependent on number of fibers received per session. The patient will not need to receive additional doses of porfimer sodium if having additional I-PDT sessions within 14 days after the previous I-PDT session as porfimer sodium is expected to be in the tumor for at least 30 days.
- Q. The intraoperative ultrasound is done for 2nd and 3rd I-PDT courses, as per physician's discretion.

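### The maximum number of light treatments per participant is stated in conflicting ways, so the recommended irradiance is not tied to a defined maximum exposure

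*Combined protocol and SAP*

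**What the plan says.** Section 10.4 provides that, where a tumor needs more than one course for full illumination, "up to three sessions of I-PDT may be performed, at the discretion of the treating physician". It adds that "treatment sessions in this study will be conducted at least 30-days apart".

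Appendix D has two further provisions. Note 17 reads "Another (one or two, total of three) laser light treatment(s) only (no additional drug) within 2-3 weeks of the initial administration of Photofrin". Note 18 reads "Patient may receive a second complete I-PDT treatment that will include drug and light administration", and its column is headed as additional treatment 2 or 3.

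Appendix D 1, which covers later treatments, says that "study participants may have up to 3 I-PDT courses". Where treating the whole tumor at once could be a health risk, Appendix D note 16 and Appendix D 1 note P say that "the current I-PDT course will be broken up into session/s". The further parts are to be illuminated within 14 days, and no number of sessions is given.

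The dose-finding rule (Table 2 in Section 10.4) counts patients with a DLT at a dose level. Section 10.3 evaluates DLTs for 30 days after the final I-PDT day. Section 19.6 tabulates toxicity by grade across dose levels and cycles, and asks for nothing by number of illuminations.

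**The concern.** The trial's dose-finding result is a light irradiance, judged by how many of at most 12 participants have a DLT. A participant contributes one yes-or-no outcome whether treated once or several times. Section 10.4 deliberately allows some variation, but there should be one upper limit. The documents do not give one, and *course* and *session* cannot settle the matter. Sections 10.4 and 11.2 use the two words interchangeably. Notes 16 and P make a session a part of a course, while both schedules define the I-PDT procedure itself as a course.

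Two physicians following different parts of the protocol could therefore give different maximum exposures at the same dose level. A later reader of the recommended irradiance could not tell how much repeated treatment it was shown to tolerate.

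**Working it through.** **Check on the design figure.** Two light levels with up to 6 participants each give 2 × 6 = 12. Four cohorts of 3 also give 12. This matches the maximum in Sections 4.0 and 19.1, and the point below does not change it.

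**The limits side by side.**

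| Place | Light treatments | Drug-plus-light treatments |
|---|---|---|
| Section 10.4 | 3 sessions, at least 30 days apart | up to 3, on the reading session = course |
| Appendix D note 17 | 3 on the initial drug dose, within 2–3 weeks of it | none added |
| Appendix D note 18 | not stated; at least 1 more | a second |
| Appendix D 1, note * | 3 courses, at least 30 days apart | up to 3 |
| Note 16 and note P | a course split within 14 days, number not stated | none added |

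**Smallest total from notes 17 and 18.** 3 on the first drug dose + at least 1 in the second complete treatment = 4. This exceeds 3 if a Section 10.4 session is one illumination. If a session is instead a whole course, Section 10.4 sets no limit on illuminations. The spacing points the same way: repeats within 2–3 weeks of the drug cannot be sessions held at least 30 days apart.

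**Link to the DLT count.** For three courses at the minimum spacing, the last is at day 60 and the DLT window closes at day 60 + 30 = 90. For one course it closes at day 30. Section 10.3 can be read literally as counting only events after the final treatment. However, its rule that holds further sessions after a DLT implies that earlier events count too. The illustration below takes the second reading.

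**Illustration.** No DLT rate is given, so assume a constant, independent risk p per full illumination and the same number k of illuminations for every participant.

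- Per-participant risk: q = 1 − (1 − p)^k.
- Chance that Level 1 ends with at most 1 DLT in 6: (1 − q)^6 + 6q(1 − q)^5. This equals the Table 2 path: 0 of 3 then at most 1 of 3, or 1 of 3 then 0 of 3.
- p = 5%, k = 3: q = 1 − 0.95³ = 0.143; chance = 0.397 + 0.397 = 0.794.
- p = 5%, k = 4: q = 1 − 0.95⁴ = 0.185; chance = 0.292 + 0.399 = 0.691.

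| Assumed p | k = 3 | k = 4 |
|---|---|---|
| 3% | 91% | 86% |
| 5% | 79% | 69% |
| 8% | 60% | 46% |

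**The case against.** The strongest reply is that this is loose vocabulary around one intended limit. Three complete courses is the prevailing figure: Section 10.4 rests on a precedent of up to three courses, and Section 11.2 and Appendix D 1 repeat it. The column heading above note 18 can be read as treatment number 2 or 3. Appendix D is titled for the case where only one course is needed, and its note 2a sends later courses to Appendix D 1. This largely stands. A reader might infer a firm clash of two against three complete treatments, but note 18 states no maximum. It speaks only of a second and needs to be aligned or explained.

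A reader might also infer that participants can receive 6 to 9 illuminations. No passage says so. Those totals come from multiplying three light treatments by two or three drug doses, or three courses by two or three sessions. Note 17 covers only the initial drug administration. The phrase "according to the same schedule parameters as the initial treatment" in note 18 belongs to the tests before and after treatment. Notes 16 and P give no number to multiply by.

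Nor do the documents support giving each split session the full risk. Those sessions treat different parts of the tumor and are meant to reduce risk.

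Finally, later courses are optional, adverse events are reviewed before each one, and Section 10.3 holds treatment after a DLT. A constant risk applied equally to everyone is therefore a simplification. Under the same 5% assumption, the fall from 97% at one illumination to 79% at three lies within Section 10.4's own limit. One agreed maximum would not remove it.

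What the reply does not answer is how note 17's light-only repeats combine with later complete treatments, or how many sessions a course may have.

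**Conclusion.** The contradiction is real and worth correcting. Section 10.4 limits a participant to three sessions. Notes 17 and 18 together permit at least four illuminations, and notes 16 and P permit split sessions of unstated number. Because the dose rule counts participants and the DLT window follows the final treatment, the recommended irradiance carries no defined maximum exposure.

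The size of the effect cannot be established. The percentages in the working rest on an assumed risk, independence and equal treatment of all participants. They show only the direction: acceptance of Level 1 becomes less likely as full illuminations increase. A reader might infer that the choice of irradiance turns on this wording, but the documents give no DLT rate and no expected number of treatments from which to conclude that.

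**What to change.** Reconcile Section 10.4, Appendix D notes 16 to 18 with their column headings, and Appendix D 1 notes * and P. The result should be one maximum number of light treatments and one maximum number of drug-plus-light treatments per participant, with the sponsor choosing both figures. Give *course* and *session* one meaning each and use them that way throughout, including Section 11.2. State whether split sessions and light-only repeats count toward the maximum.

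Beside each Table 2 DLT count, list the number of illuminations and of drug doses each participant received.

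The cost is a wording amendment, one more column in the DLT listing and somewhat less physician discretion. No participants or procedures are added, and the maximum of 12 stands.

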10.2.2 Pre-treatment Planning

For all participants receiving I-PDT, a standard diagnostic head and neck scan with CT or MRI, will be obtained within 4 weeks prior to I-PDT. This imaging will be used for pre-treatment planning that will be conducted at [name] laboratory at Roswell Park, with the treating physician at each participating site.

The pretreatment planning will be carried out by following these steps:

- 1. If possible, clinically approved surface fiducial markers (using removal stickers) will be affixed to the skin (at the region of the tumor) prior to CT or MRI, to assist in the guidance of laser fibers, as described in Oakley et al. 2017(40).
- 2. The scans will be de-identified, linked to a subject ID, and copied on CD or transferred via secure network to [name] laboratory, 5-14 business days prior to the scheduled I-PDT.
- 3. The treating physician will use the CT or MRI scans and the image reconstruction model for defining the clinical target volume (CTV).
- 4. Image analysis software will be used to reconstruct the CT or MRI scans to generate a computer model of tumors and adjacent anatomy as we described in Oakley et al. 2015 and Oakley et al. 2017.(40, 41)
- 5. The treating physician will also use the computer model to recommend the number and location of closed-end transparent catheters that can be safely placed within the CTV.

- 6. The computer model (of the CTV) will be imported into a finite element modeling (FEM) software, to calculate the light intensity (mW/cm) and energy (J/cm) that will be required to be delivered by each fiber, so that 100% of the CTV receives the target light dose (i.e. computed fluence rate >8.6 mW/cm² and fluence >45 J/cm²) as much as possible.
- 7. The FEM simulations will be presented to the treating physician for approval of the treatment plan at least 5 business days prior to the I-PDT.

Note: If subjects are scheduled to receive additional I-PDT courses (at least 30 days from the previous I-PDT, see Section 10.4), per the physician's discretion, pre-treatment planning procedures for additional I-PDT courses are per the physician's discretion.

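### Three separate inconsistencies: re-illumination intervals that conflict, a DLT window (10.3) that leaves out events its own hold rule calls DLTs, and an SAE window (19.3) anchored to standard of care

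*Combined protocol and SAP*

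**What the plan says.** **Intervals.** Section 10.4 cites the labelled use in other cancers, "up to three courses of PDT with Photofrin® each separated by at least 30 days", and concludes that "treatment sessions in this study will be conducted at least 30-days apart". Section 10.2.2 repeats the minimum for additional courses: "at least 30 days from the previous I-PDT, see Section 10.4". Appendix D 1 counts it "at least 30 days from the previous illumination procedure". Against this, Appendix D note 16 and Appendix D 1 note P let a large tumor be treated in parts, with "additional I-PDT session/s within 14 days after the initial I-PDT session". Appendix D note 17 allows "laser light treatment(s) only (no additional drug) within 2-3 weeks of the initial administration of Photofrin", under a column that labels this a second course within 2-3 weeks of Day 0. Another Appendix D column puts full drug-plus-light retreatment no earlier than 6 weeks after the last session.

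**Cap.** Section 10.4: "up to three sessions of I-PDT may be performed". Appendix D 1: "study participants may have up to 3 I-PDT courses".

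**DLT and primary safety window.** Sections 10.3 and 8.1 both use the 30 days after the final I-PDT. Section 10.3 then adds a hold rule: after a DLT, further sessions wait for resolution and for drug clearance. Section 11.2 has earlier adverse events reviewed before the next course. Table 2 counts patients with a DLT and does not say which course counts.

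**SAE analysis and AE reporting.** Section 19.3 counts SAEs for 30 days from first SoC treatment, or from the last I-PDT if no SoC is given, and applies sequential boundaries that can halt accrual. Appendix D notes 13-14 and Appendix D 1 note M also use the SoC anchor. Section 17.3 collects AEs from the start of intervention to 30 days after the last one, and 19.6 tabulates toxicity by grade across all cycles.

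**The concern.** Retreatment is at the physician's discretion, and safety is the primary objective, so three things need one clear rule each: when a patient may be re-illuminated, which events make that patient a DLT, and which events feed the stopping boundary. Each has two rules.

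A physician deciding on a light-only session at 2-3 weeks has one text that permits it and one that forbids it. A related grade 4 event that resolves and is followed by retreatment is a DLT under one paragraph of 10.3 and outside the window in another. When SoC follows I-PDT, the 19.3 window opens only after the period in which local reactions to the procedure would be looked for first. With at most 12 patients, these questions should not be settled after the event has happened.

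**Working it through.** Take first illumination as day 0. Porfimer is given 48 ± 8 hours earlier (10.2.1), about day -2.

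**1. Intervals**

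| Source | What it governs | Limit |
|---|---|---|
| 10.4 | sessions | at least 30 days |
| Appendix D 1, opening note | any illumination | at least 30 days |
| Appendix D note 16, D 1 note P | further sessions, same drug dose | at most 14 days after the first session |
| Appendix D note 17 | light only, same drug dose | 2-3 weeks after drug |
| Appendix D column | drug plus light | at least 6 weeks (42 days) |

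The latest light-only day under note 17 is 21 days after drug. In days after first light this is 21 - 56/24 = 18.7 to 21 - 40/24 = 19.3. Both 14 and 19.3 are below 30, so these sessions cannot satisfy 10.4 or Appendix D 1 as worded. The 42-day minimum does satisfy 30 days; it is a second, stricter figure rather than a contradiction. On the cap, a course split into two sessions uses two of three under 10.4 and one of three under Appendix D 1.

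**2. The 10.3 window**

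Let F be the day of the final I-PDT. The literal window is F to F + 30.

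| Minimum gap | One further course | Two further courses |
|---|---|---|
| 30 days | F = 30, window 30-60 | F = 60, window 60-90 |
| 42 days | F = 42, window 42-72 | F = 84, window 84-114 |

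*Case A.* A related grade 4 event on day 10 resolves by day 25, and the patient is retreated on day 40, which the 30-day rule allows. The window is days 40-70. The hold rule calls the event a DLT; the window excludes it.

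*Case B.* Retreatment is planned for day 42, a related grade 4 or 5 event occurs on day 35, and retreatment is cancelled. The final I-PDT is then day 0, the window is days 0-30, and the event is outside it.

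The short-interval sessions do not add a further Case A. Note 16 expects drug in the tumor for at least 30 days, so clearance comes no earlier than about -2 + 30 = day 28, and the hold rule bars a 14-day or 2-3 week session after a DLT.

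**3. What one patient changes in Table 2**

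The stated maximum is reproduced: 2 dose levels × 6 = 4 cohorts × 3 = 12.

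- 1/3 read as 0/3: no change, since either result puts three more patients on level 1.
- 2/3 read as 1/3: three more on level 1 instead of three on level -1.
- 2/6 read as 1/6: level 1 meets the criterion for the recommended Phase 2 dose, which 2/6 does not.

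**4. The 19.3 window**

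Let S be the days from the last I-PDT to first SoC. The 8.1 window is 0 to 30 and the 19.3 window is S to S + 30. The overlap is max(0, 30 - S), and the share of the 8.1 window missed is S/30 for S < 30 and 100% for S ≥ 30. The documents give no S, so these values are illustrations only.

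| S (days) | Overlap (days) | Missed |
|---|---|---|
| no SoC | 30 | 0% |
| 7 | 23 | 23% |
| 14 | 16 | 47% |
| 21 | 9 | 70% |
| 28 | 2 | 93% |
| 30 or more | 0 | 100% |

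Sections 17.3 and 17.4.1 also end reporting when a new treatment starts. If SoC counts as a new treatment, which the protocol does not say, routine reporting closes as the 19.3 window opens.

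**The case against.** **On intervals**, much of this is terminology. Section 10.4 derives its 30 days from labelled courses, and notes 16 and P treat sessions within 14 days as parts of one course. That is probably the intent. But 10.4 applies the minimum to sessions, Appendix D 1 to any illumination, and Appendix D calls the 2-3 week light-only treatment a course, so the intended reading is not what the text says.

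**On DLTs**, a reader might infer that the Case A event has no place in Table 2. That goes too far: the hold rule names it a DLT, Table 2 counts patients with a DLT, and events are reviewed before each further course (11.2) and continuously (19.7). Counting it is the natural reading. What stands is that the explicit window says otherwise and nothing resolves the two. Nor does any text give DLTs a SoC anchor; that applies to the SAE analysis and AE reporting only.

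**On SAEs**, a reader might infer that events soon after I-PDT go unanalysed. They do not: 17.3 collects them and 19.6 tabulates them. They fall outside the 19.3 window, and so outside the boundary as defined. A reader might also equate Appendix D's clinic visit (Day 1 of SoC) with the 11.5 visit at 1-4 weeks and conclude that 23% to 93% of the window is lost. Appendix D has a separate 1-week visit that also fits 11.5, so the match is unsupported. Appendix D 1 note N, which puts Phase 1 patients off treatment 30 days after the last I-PDT, could equally mean S ≥ 30.

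**Conclusion.** The plan is inconsistent as written on all three matters. They are independent: correcting the intervals would not settle the DLT count, and correcting the SoC anchor would settle neither of the others.

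The interval conflict is certain for split and light-only sessions. The DLT exposure is narrow: a resolved grade 4 event followed by retreatment (Case A), or a related event more than 30 days after an I-PDT whose planned retreatment is then cancelled (Case B). It would therefore be wrong to assume that every event that ends treatment is captured. The consequence of one omitted patient is a changed Table 2 action at 2/3 or 2/6. No probability can be attached, because the documents give no DLT rate, retreatment rate or share of DLTs that resolve; the window dates are calendar arithmetic, not risks. The SAE shortfall is S/30 up to day 30 and complete from then on, with S unknown, and it arises only when SoC is given.

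**What to change.** - In 10.4, define a *session* (light only, same drug dose, within one stated limit) and a *course* (new drug plus light). Apply one minimum interval to courses in 10.2.2, 10.4, Appendix D and Appendix D 1. Rename the light-only second-course column as a session, and say whether the cap of three counts sessions or courses.
- In 10.3 and 8.1, run the window from the first porfimer dose (the start of intervention, as in 17.3) to 30 days after the last I-PDT. State that any qualifying event in it counts the patient once in Table 2. Starting at the drug rather than the light also covers the roughly 48 hours between them.
- Use the same window in 19.3, Appendix D notes 13-14 and Appendix D 1 note M. Align the new-treatment cutoff in 17.3 and 17.4.1 so that starting SoC does not close reporting within the 30 days.

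The cost is amendment wording. Section 17.3 already collects most of what is needed; the new-treatment cutoff is the exception. One downside should be stated: time at risk for a DLT then depends on discretionary retreatment, so report sessions and drug doses per patient beside the DLT table.
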